Effects of **R**emote **I**schemic Pre-Conditioning on Neurologic
Complications in Adult Ischemic **M**oyamoya Disease Patients
Undergoing **E**ncephaloduroarteriosynangiosis (**RIME**)

—— A Prospective, Multi-center, Randomized Controlled Trial ——

Study Protocol

Neurosurgical Principal Investigator

[name]

Professor of Neurosurgery

Beijing Tiantan Hospital, Capital Medical University, Beijing

Peking University International Hospital, Peking University, Beijing

[name]

Professor of Neurosurgery

Beijing Tiantan Hospital, Capital Medical University, Beijing

Peking University International Hospital, Peking University, Beijing

[name]

Professor of Neurosurgery

Beijing Tiantan Hospital, Capital Medical University, Beijing

Peking University International Hospital, Peking University, Beijing

August 20, 2019

1. Protocol Synopsis

Title	Effects of Remote Ischemic Pre-Conditioning on Neurologic Complications in Adult Ischemic Moyamoya Disease Patients Undergoing Encephaloduroarteriosynangiosis
Acronym	RIME
Objectives	
• To evaluate the safety of remote ischemic preconditioning in adult ischemic MMD patients undergoing indirect revascularization;• To evaluate the clinical benefit of remote ischemic preconditioning in adults with ischemic MMD who underwent indirect revascularization.
Study Design	
This study was a multi-center, prospective, randomized, controlled trial of randomized (1:1) adult ischemic MMD patients undergoing indirect revascularization into two groups:
 
1. RIPC group Remote limb ischemic preconditioning (RIPC) is consisted of five 5-min cycles of bilateral arm ischemia/reperfusion, it is induced by a sphygmomanometer placed on bilateral arm and inflated to 200 mmHg for 5-min followed by deflating the cuff for 5-min, patients in the RIPC group will do it twice a day for at least five days before EDAS.2. sham RIPC group Sham RIPC group is consisted of five 5-min cycles of bilateral arm ischemia/reperfusion, induced by a sphygmomanometer placed on bilateral arm and inflated to 60 mmHg for 5-min followed by deflating the cuff for 5-min, they will do it twice a day for at least five

	days before EDAS.
Primary endpoint	
 • All cerebrovascular events (ischemic stroke, cerebral hemorrhage, transient neurological deficits) within 30 days post-surgery • All death or dependent (mRS > 2) within 30 days post-surgery
Secondary endpoint	
 • The severity of the ischemic stroke after surgery • Number of patients occurred restroke at Follow-up Period • Number of patients dependent or death at follow-up period • Number of patients with improved neurological function at follow-up period • Perfusion status of patients at follow-up period • Number of patients with any side effects of remote ischemic preconditioning (RIPC) treatment.
Inclusion Criteria	
 • Patients who diagnosed with moyamoya disease • Adults 18 to 65 years of age • The onset symptoms manifested as ischemic symptoms (TIA or stroke) or atypical symptoms (headache, epilepsy or asymptomatic) • Able to receive the necessary imaging examination • Patients who pre-agreed to the study
Exclusion Criteria	
 • Prior cerebral hemorrhage history • Other brain or cerebrovascular disease • Previous history of revascularization surgery • Dependent (mRS > 2) • Receive other type of revascularization surgery • Peripheral blood vessel disease (especially subclavian arterial and upper limb artery stenosis or occlusion).

	
 • Patients who do not agree with the study
Sample Size	
Sample size and power were calculated based on previous studies and postoperative neurological complications, which were much better to indicate the efficacy of RIPC. We calculated the simple size and power with PASS, version 11 (NCSS, LLC, Kaysville, UT, USA). We expected ≈10% of subjects in the RIPC group and 20% of subjects in the other 2 groups would have new postoperative neurological complications. The intended target sample size was 328 subjects allowing 15% loss to follow-up and with 90% power and an α of 0.05 (2-sided) of significance.

Follow-up	
The face-to-face interview will be performed by study neurologists at discharge, at 6 months and at 12 months (or by telephone) after the recruitment of patients.

2. Study Rationale

2.1 Background

Moyamoya disease (MDD) is a chronic ischemic cerebrovascular disease characterized by chronic progressive stenosis of the bilateral internal carotid artery.¹ Chronic progression of the disease can lead to the formation of abnormal vascular networks, including vascular network compensation for the formation of the skull base and the initial pathological changes in the area of cerebral infarction.² MMD is common among East Asians, including Japan, South Korea and China.³⁻⁵ The clinical manifestations of MMD are mainly divided into two types in the Asian population: ischemic and hemorrhagic. The ischemic type accounts for about 70%, and the

hemorrhagic type accounts for about 30%.^{6,7}

For the treatment of patients with MMD, the main purpose is to prevent further stroke events and reduce the rate of recurrent stroke.⁸ There are two types of treatment for patients with MMD: surgery and conservative treatment.⁹ Surgical treatment includes direct revascularization and indirect revascularization. Surgical treatment has been widely recognized for reducing ischemic MMD re-stroke, but there is still controversy about hemorrhagic MMD.^{10,11} Indirect revascularization is a simpler, less laborious technique than direct revascularization requiring manual anastomosis of extracranial donor vessels and intracranial recipient vessels, with a lower risk of postoperative complications.^{12,13} Furthermore, many recent studies demonstrated that the long-term efficacy of indirect revascularization has no significant difference with direct revascularization.¹³⁻¹⁵ However, due to insufficient blood supply to the brain in patients with MMD, the vascular reactivity of the cerebral vessels is decreased,¹⁶ leading to poor tolerance to hemodynamic changes.¹⁷ Cerebral hypoperfusion may occur after indirect revascularization surgery, leading to postoperative ischemic events and postoperative neurological deterioration,¹² which may increase postoperative morbidity and mortality. Therefore, patients undergoing cerebral revascularization require an effective neuroprotective strategy.

Several animal and human studies have shown that non-fatal ischemic injury has an overall protective effect on pretreated tissues and other distal organs, which is called distal ischemic preconditioning (RIPC).^{18,19} RIPC has cardioprotective effects on patients undergoing cardiac surgery.²⁰ In terms of neuroprotection, RIPC reduces

recurrence of transient ischemic attack (TIA), improves recovery and increases cerebral perfusion in patients with a history of stroke or TIA and intracranial stenosis.²¹ Vasodilation prevents ischemia in patients with subarachnoid hemorrhage.²²

When RIPC is applied to adult ischemic MMD patients undergoing indirect cerebral revascularization, whether it can reduce the incidence of postoperative neurological complications in MMD patients and improve the neurological prognosis of patients with MMD, there is still no evidence-based medical evidence.

2.2 Research status

Many literatures have reported risk factors for neurological complications in patients with MMD after revascularization,^{12, 27, 28} however, there is a lack of effective measures and clear criteria for how to reduce the incidence of neurological complications after revascularization in patients with MMD. A recent study reported the effect of combined remote ischemic treatment on neurological complications after STA-MCA anastomosis in patients with MMD.²⁹ This study demonstrated the potential of combined RIPC and RIPostC to reduce neurologic complications and the duration of hospitalization in patients undergoing STA-MCA anastomosis for MMD. However, since this study is a single-center study and only 108 patients were enrolled, the effectiveness of RIPC remains to be confirmed. In addition, the effect of direct revascularization varies greatly depending on the surgeon's experience and technique. When conducting a multicenter study, the results may be biased. At the same time, because this study enrolled MMD patients undergoing direct revascularization, it is

unclear whether RIPC can reduce the incidence of postoperative neurological complications in adults with ischemic MMD undergoing indirect revascularization. Whether RIPC is effective enough in adult ischemic MMD patients undergoing indirect revascularization to reduce postoperative neurological complications and improve prognosis? The current research quality is not sufficient to support clinical decision making. In adult ischemic MMD patients undergoing indirect revascularization, prospective clinical trials to confirm the clinical benefits and risks of RIPC procedure have become clinical problems that need to be addressed.

3. Primary Aim

- To evaluate the safety of remote ischemic preconditioning in adult ischemic MMD patients undergoing indirect revascularization
- To evaluate the clinical benefit of remote ischemic preconditioning in adults with ischemic MMD who underwent indirect revascularization

References

3. Kuriyama S, Kusaka Y, Fujimura M, Wakai K, Tamakoshi A, Hashimoto S, et al. Prevalence and clinicoepidemiological features of moyamoya disease in japan: Findings from a nationwide epidemiological survey.


4. Study Plan and Procedure

Study Design and Flow Chart

This study was a multi-center, prospective, randomized, controlled trial of

randomized (1:1) adult ischemic MMD patients undergoing indirect revascularization into two groups:

1. RIPC group

Remote limb ischemic preconditioning (RIPC) is consisted of five 5-min cycles of bilateral arm ischemia/reperfusion, it is induced by a sphygmomanometer placed on bilateral arm and inflated to 200 mmHg for 5-min followed by deflating the cuff for 5-min, patients in the RIPC group will do it twice a day for at least five days before EDAS.

2. sham RIPC group

Sham RIPC group is consisted of five 5-min cycles of bilateral arm ischemia/reperfusion, induced by a sphygmomanometer placed on bilateral arm and inflated to 60 mmHg for 5-min followed by deflating the cuff for 5-min, they will do it twice a day for at least five days before EDAS.

5. Study Endpoints

5.1 Primary Endpoint

- All cerebrovascular events (ischemic stroke, cerebral hemorrhage, transient neurological dysfunction) within 30 days post-surgery
- All death or dependent (mRS > 2) within 30 days post-surgery

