In order to prevent errors in the research due to the interpretation technique, this study set up a decision-making committee to uniformly judge the imaging data of the patients enrolled. Two experienced neuroimaging physicians conducted mutual blind interpretation, and the results of the inconsistent report should be ranked third. The senior neuroimaging chief physician will conduct a trial and finally submit true and reliable imaging results for all cases. The interpreter does not participate in the study design and does not know the patient's clinical information.

11. Bio sample test

Blood samples were drawn from the cubital vein; the points of measurement included baseline, pre-EDAS, right 1 hour and 24 hours post-EDAS. The collected blood samples were sent for examination, and plasma neuron specific enolase (NSE) and human S protein 100B (S-100B) levels were examined in the test samples.

11. Schedule of Follow-up and Post-study Follow-up Period

All patients will be followed up until the primary endpoint or the end of the trial.

Complete endpoint information will be obtained with the best effort irrespective of patient study status, unless patients withdraw consent to participate the trial. The face-to-face interview will be performed by study neurologists at discharge, at 6 months and at 12 months (or by telephone) after the recruitment of patients.

Visits	Windows	Definition
Randomization	0 day	Study Day 0 day
At discharge	0 day	Based on the number of hospitalization days
At 6 months	14 days	Day 166-194
At 12 months	30 days	Day 330-390

12. Quality Assurance

Periodic monitoring and auditing will be performed at each site to ensure that data generated during the study reflect what is specified in the protocol, and data consistence by comparing data in the case report form (CRF) and data collected in source documents for (CRF vs. source documents). If patients who have events go to non-study sites for treatment, source documents will be photocopied for review. It should be guaranteed that the study investigators and relevant study personnel are available during the monitoring visits and possible audits.

13. Statistical Consideration

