Protocol should be submitted to the Ethics Committee (IRB/IEC). It should also be informed of any event likely to affect the safety of patients or the continued conduct of the Clinical Trial, in particular any change in safety. All updates to the Investigator's Brochure will be sent to the Ethics Committee (IRB/IEC). If requested, a progress report will be sent to the Ethics Committee (IRB/IEC) annually and a summary of the Clinical Trial's outcome at the end of the Clinical Trial.

16. Safety Outcomes Assessment

The following adverse events were defined as safety outcomes: (1) elevation of plasma NSE and S-100B levels beyond normal limits after RIPC and sham RIPC procedure; (2) inability to tolerate RIPC or sham RIPC procedure that leads to the discontinuation from the study; (3) objective signs of tissue or neurovascular injury resulting from RIPC and sham RIPC procedure. An inspection that was done by staffs blinded to the study protocol included palpation of distal radial pulses, visual inspection for local edema, erythema and skin lesions, and palpation for tenderness. These safety outcomes were evaluated by observers blinded to the treatment assignment, and any suspicious adverse event associated with RIPC or sham RIPC procedure was reported to the investigators.

APPENDIXS

Study Flow Chart

Schedule of Visits and Test

	Visit 1	Visit 2	Visit 3	Visit 4	Event visit
Assessments	Screening/Randomize	At discharge	At 1 year ± 1 month	Every 12 months ±1 month	
Informed Consent	✓				
Eligibility criteria	✓				
Patient Randomization	✓				
Relevant medical history	✓				
Demographics	✓				
MRI before Surgery	✓				
CTP before Surgery	✓				
DSA before Surgery					
Vital signs	✓				✓
Modified Rankin Score	✓	✓	✓	✓	✓
MRI after surgery		✓	✓	✓	
CTP after surgery		✓	✓	✓	✓
DSA after surgery		✓	✓		✓
Current Medications	✓	✓	✓	✓	✓
Endpoints		✓	✓	✓	✓

modified Rankin Scale

The modified Rankin Scale (mRS) is a scale commonly used for measuring the degree of disability or dependence in the daily activities of individuals who have suffered a stroke, and it has become the most widely used clinical outcome measure for stroke clinical trials.

Description	Score (select one)
No symptoms at all	0 
No significant disability despite symptoms; able to carry out all usual duties and activities	1 

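### Strokes, haemorrhages, transient deficits and deaths between randomisation and EDAS, when all conditioning is given, are not compared by arm in any primary endpoint or listed safety outcome

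*Combined protocol and SAP*

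**What the plan says.** **Timing of treatment.** Section 4 (Study Plan and Procedure) puts the whole intervention before surgery: "patients in the RIPC group will do it twice a day for at least five days before EDAS", and for sham, "they will do it twice a day for at least five days before EDAS". The visit table in the follow-up section labels randomisation "Study Day 0 day".

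**Primary endpoints.** Section 5.1 has two, both starting at the operation: "All cerebrovascular events (ischemic stroke, cerebral hemorrhage, transient neurological dysfunction) within 30 days post-surgery" and "All death or dependent (mRS > 2) within 30 days post-surgery".

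**Safety.** The first aim in Section 3 is "To evaluate the safety of remote ischemic preconditioning in adult ischemic MMD patients undergoing indirect revascularization". Section 16 begins "The following adverse events were defined as safety outcomes" and lists three:
- "elevation of plasma NSE and S-100B levels beyond normal limits after RIPC and sham RIPC procedure";
- intolerance of the procedure that leads to discontinuation;
- objective tissue or neurovascular injury resulting from the procedure. The inspection described is of pulses, swelling, skin and tenderness.

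Any other adverse event is reported to the investigators if it is suspected to be associated with the procedure.

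**Secondary endpoints.** Section 5.2 includes side effects of RIPC, restroke, and dependency or death. The last two are counted over a follow-up period whose start is not given.

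**Patients not operated on.** Section 13.2 names no analysis population, and no section says how a randomised patient who never has EDAS is analysed.

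**The concern.** Treatment lasts at least five days and ends before the primary clock starts. A stroke, transient deficit or death in those days is the gravest harm that conditioning could do. Section 2.1 itself says that these patients have reduced cerebrovascular reactivity and tolerate haemodynamic change poorly. Yet the plan specifies no comparison of these events by arm that is free of someone's judgement about cause. Both the side-effects endpoint and the reporting rule in Section 16 require the event to be attributed to, or suspected of being associated with, the cuff.

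There is a second consequence. A patient with a pre-operative event may not be operated on. The 30-day endpoints then apply only to those who reach surgery. That step comes after randomisation and could be affected by treatment, so the comparison would no longer be of the groups as randomised.

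**Working it through.** **1. Which outcomes reach a pre-EDAS event?**

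| Outcome | Counts a pre-EDAS stroke, haemorrhage, transient deficit or death? |
|---|---|
| Primary 1, cerebrovascular events (5.1) | No; starts at surgery |
| Primary 2, death or mRS > 2 (5.1) | Not the event; lasting disability in an operated patient could show as mRS > 2 |
| Biomarker rise (16) | No; a laboratory value, even if a stroke might raise it |
| Intolerance (16) | Not named |
| Tissue or neurovascular injury (16) | Not named; must result from the procedure, and the inspection is of the limb |
| Side effects of RIPC (5.2) | Only if attributed to RIPC |
| Restroke; dependency or death (5.2) | Unclear; start of period not defined |

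**2. Inputs for illustration.** The plan's post-surgery risks are 10% (RIPC) and 20% (control), with 328 patients randomised 1:1 (Section 13.1 and Synopsis), so 164 per arm. The plan gives no figure for pre-operative events, so there is none to reproduce. The risk q of an event between randomisation and EDAS is an assumption throughout. (The 328 does not itself reproduce as a total from the stated inputs. That is a separate matter, and nothing here depends on it except the use of 164 per arm.)

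**3. Benefit counted from randomisation.** With post-surgery risk p, the risk from randomisation is q + (1 − q)p.
- q = 5% RIPC, 1% sham: (0.01 + 0.99 × 0.20) − (0.05 + 0.95 × 0.10) = 0.208 − 0.145 = 0.063.
- q = 1% RIPC, 5% sham: (0.05 + 0.95 × 0.20) − (0.01 + 0.99 × 0.10) = 0.240 − 0.109 = 0.131.

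The post-surgery endpoint shows 0.10 in both cases.

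**4. No net effect.** Let the total risk be 20% in each arm, and suppose that every patient with a pre-operative event leaves the post-surgery window. The risk seen after surgery is then p = (0.20 − q)/(1 − q): 0.200 at q = 0, 0.1919 at 1%, 0.1753 at 3% and 0.1579 at 5%. Let d be the sham risk minus the RIPC risk. The chance of a significant result favouring RIPC is Φ[(d − 1.96·s₀)/s₁], where s₀ and s₁ are the pooled and unpooled standard errors with 164 per arm.

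| q sham | q RIPC | d | s₀ / s₁ | False-benefit rate |
|---|---|---|---|---|
| equal | equal | 0 | – | 2.5% |
| 1% | 3% | 0.0167 | 0.0428 / 0.0427 | 5.8% |
| 1% | 5% | 0.0340 | 0.0420 / 0.0419 | 12.5% |
| 0% | 3% | 0.0247 | 0.0431 / 0.0431 | 8.3% |
| 0% | 5% | 0.0421 | 0.0423 / 0.0423 | 16.7% |

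Reducing each arm by the patients who leave (164 × (1 − q)) moves these rates by less than half a percentage point.

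**The case against.** **The window matches the question.** The trial asks about postoperative complications and is sized on them. This stands, and it is why the 30-day endpoints should remain primary. It does not meet the separate safety aim.

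**Some events may be caught elsewhere.** A reader might infer that pre-EDAS events count nowhere. The documents do not support that. The visit table starts at randomisation, later visits are timed from recruitment, and endpoint information is to be completed whatever the patient's study status. On that reading, restroke, dependency and death could include pre-EDAS events by arm without attribution. But the start of the follow-up period is not stated, and transient deficits are in neither endpoint. A disabling pre-EDAS stroke in an operated patient could show as mRS > 2, but as a status after surgery rather than as an event during treatment.

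**There is other oversight.** Blood is drawn at baseline and before EDAS, and the DSMB reviews safety data for both arms about every three months. So the period is not unmonitored. Neither provision specifies a comparison of clinical events for the final analysis.

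**The bias is hypothetical and could go either way.** A reader might infer that the plan favours RIPC. The documents do not support that either. With no net effect and equal pre-operative rates there is no bias. Section 2.1 cites evidence that RIPC reduces recurrent TIA; if it lowered pre-operative events, the present window would understate the benefit. The 8–17% false-benefit range needs a sham rate of zero, and all the non-zero illustrations need affected patients to leave the window.

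**Conclusion.** The point holds in this form: clinical events during the treatment period are not compared by arm in any primary endpoint or listed safety outcome, and whether two secondary endpoints would include them cannot be told from the text. That rests on the wording alone.

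The effect on the efficacy comparison is of unknown size and direction, because no pre-operative rate is given and nothing is said about patients who do not reach EDAS. As illustrations only: with no net effect, the false-benefit rate stays at 2.5% with equal rates. With 3–5% pre-operative events under RIPC it is about 6–12.5% if sham has 1%, and about 8–17% if sham has none. With post-surgery risks of 10% vs 20%, the benefit from randomisation ranges from 6.3 to 13.1 points across the two mirror-image cases, against 10 after surgery.

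This should be corrected, but it does not invalidate the primary analysis.

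**What to change.** 1. Add a fourth safety outcome to Section 16: any ischaemic stroke, cerebral haemorrhage, TIA/TND or death from randomisation to EDAS, regardless of attribution, compared by arm in all randomised patients. The appendix already defines the cerebrovascular events.
2. Add to Section 13.2 a supportive analysis of the primary endpoints counted from randomisation to day 30 after EDAS. Include patients never operated on, with a fixed matching window for them set in advance.
3. State in Section 5.2 that the follow-up period starts at randomisation.

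The 30-day post-surgery endpoints stay primary and the sample size is unchanged.

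The cost is plan wording, one more table and modest extra event collection before surgery. The appendix schedule already has an event visit. The documents do not say where cuff sessions take place or who supervises them, so the effort of collecting events cannot be taken as nil. Numbers will be small: at an assumed 1% in both arms, about 3 of 328 patients (328 × 0.01 = 3.3). Even no events among 164 leaves a one-sided 95% upper limit of 1.8% (1 − 0.05^(1/164)). The table should therefore give counts and confidence intervals and not be read as a powered test.
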